### 9.9 Missing Data

In spite of the relatively short follow-up of 12 months, a nontrivial loss-to-follow-up is inevitable in a study of HD due to high rates of death, transplant, and patient transfer to non-participating facilities. In the HEMO Study the combined loss-to-follow-up from death, transplant, and transfer was approximately 18% at 1 year.

Because all methods for accounting for missing data depend on untestable assumptions [Verbeke, 2000], efforts will be made to minimize missing data in the study design and conduct of the trials [Allison, 2001]. These include: 1) continuing data collection after safety stop-points or patient-termination of the treatment regimens, 2) provisions to obtain the key outcome results at a later time point should the patient be hospitalized at the target time for the visits, 3) monitoring and feedback regarding missing data throughout the trial, and 4) oral administration of questionnaires.

Analytically, including prognostic baseline covariates and the early 4-month follow-up assessment should also reduce the chance of significant bias from missing data under the restricted maximum likelihood approach we propose. [2014 FHN Archive Note: FHN Executive Committee dropped prognostic covariates from the analyses.] In this approach, bias from missing data at the 12-month assessment is reduced to the extent that relationships between the unobserved values of missing responses and the probability of missingness can be accounted for by either the baseline factors or the observed 4-month responses. Nonetheless, some bias due to informative censoring [Little, 1995] is probably inevitable. Therefore, we plan to use a pattern mixture approach [Little, 1995] to perform sensitivity analyses of the estimated treatment effects under a range of assumptions regarding the association of the censoring times with the values of the missing responses [Daniels, 2000].

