#### 2.7 Baseline Evaluation

The purposes of the baseline evaluation are to provide subjects with further information regarding the study, collect detailed data on eligibility and exclusion criteria (including practical issues such as transportation), and document baseline characteristics and clinical information to allow stratification and assessment of important baseline prognostic variables, as well as enable pre- and post-study comparisons of specific outcomes between treatment groups. *[2014 FHN Archive Note: FHN Executive Committee dropped prognostic covariates from the analyses.]* In addition, some of the characteristics assessed will enable observational comparisons with the Nocturnal Study being conducted in parallel with this trial. The length of the baseline evaluation period will be three to fifteen weeks.

Baseline Visits will be labeled as B1 visits. The baseline assessment will include two kinetic modeling sessions, separated by at least one week (see Section 3) and labeled as the B1 and B2 visits. Key biochemical tests, including predialysis serum albumin and pre- and post-dialysis serum urea nitrogen, creatinine, and phosphorus will be obtained from local laboratories for both baseline kinetic

modeling sessions. Derived kinetic modeling parameters and the pre-dialysis albumin and phosphorus concentrations will be averaged to determine the actual assigned baseline value. A timed urine collection (minimum 18 hours) will be obtained during the interdialytic interval preceding a dialysis session, preferably midweek for subjects producing urine prior to a baseline kinetic modeling session for evaluation of the residual renal function exclusion criterion. During the baseline period, participants will also be asked to travel to and from the HD unit for 6 consecutive days (i.e., on 3 HD days and on 3 intervening non-HD days), to determine if they are able to arrange and tolerate daily travel should they be randomized to the frequent arm of the trial. On the days subjects travel to and from the dialysis unit but do not receive dialysis (before randomization), they will not be required to stay at the dialysis unit for an extended period.

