# 2.8 Randomization of Trial Participants

Once the baseline evaluation is completed and eligibility is verified, consenting subjects will be randomly allocated in a 1:1 allocation to conventional or daily HD. The randomization schedules will be prepared by the Data Coordinating Center (DCC) prior to the start of recruitment.

Randomization will be stratified by Clinical Center and by diabetes status. Randomly permuted blocks of random sizes will be used to help balance numbers of participants assigned to both treatment regimens. This method guarantees that at no time during randomization will the participants in the individual groups be grossly unequal.

The randomization process will be centrally administered. All randomization schedules will remain confidential and known only by members of the Data Coordinating Center staff.

Once all baseline period studies have been completed, the forms corresponding to these studies have been received by the Data Coordinating Center, and the forms have been checked to be sure the patient meets eligibility requirements, the Principal Investigator or the study coordinator shall access the interactive randomization program. The program will verify through a defined set of questions that the participant is eligible and ready to be randomized and provide a randomized treatment assignment for that participant based upon his or her stratum. The randomization assignment will be displayed on the screen and emailed to the Clinical Center.

Randomization marks the participant's official and irrevocable entry into the Follow-up Period. Once a participant has been randomized, efforts will be made to conduct all evaluations irrespective of whether the subject starts the study treatment regimen or not, how long the patient continues on the

study treatment regimen, and how well the patient adheres to the study treatment regimen (see Section 7). These efforts should continue until termination of the Follow-up Period.

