where  $\Delta Y_t$  denotes the change in the response variable from baseline to time t, Trt is an indicator variable for the daily treatment intervention,  $Y_0$  is the baseline value of the response variable, the  $S_i$ are indicator variables for the Clinical Centers, the  $F_i$  are the two pre-specified baseline covariates age, and diabetic status, and the  $\varepsilon_t$  are random residuals at t=4 and 12 months. The primary focus of the model will be to estimate the treatment effect  $\beta_{1t}$  as accurately as possible; the remaining terms are included to reduce residual variability and reduce bias from missing data. The model will be fit by restricted maximum likelihood (Harville 77) assuming an approximate normal distribution and with an unstructured covariance matrix for the residuals at the two time points. The change in the LV mass from baseline to its single follow-up assessment at 12 months will be analyzed by restricting the basic model to one time point, which simplifies to traditional analysis of covariance. In addition to evaluating the effects of the treatment interventions on LV mass, in grams, the effects of the interventions on the percentage change in LV mass will also be considered in secondary analyses.

The target sample size of 250 patients is sufficient that inferences for the fixed effect terms in these analyses will remain valid with moderate departures from normality (Verbeke 97). However, standard diagnostics will be performed and simulations conducted to address this issue, and modifications to the model will be made if necessary.

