# 9.6 Analysis of Non-Access Hospitalization Rate or Death

The effects of the treatment interventions on the rate of non-access hospitalizations or death will be analyzed by treating the non-access hospitalizations and death as correlated event-time outcomes under a semi-parametric survival analytic framework. An Anderson-Gill model for recurrent events will be used to characterize the effects of the interventions on the intensity rate for the non-access hospitalizations, and a Cox-proportional hazards model will be used to characterize the effects of the interventions on the hazard rate for mortality. The joint analysis of both outcomes will be stratified by type of outcome (non-access hospitalization vs. mortality) to allow for potential differences between the baseline hazard function for mortality and the baseline intensity function for non-access hospitalizations. The models for both outcomes will be stratified also by Clinical Center, with treatment group and the pre-specified covariates included as independent variables. A common treatment effect will be modeled for both outcomes in order to produce a pooled estimated treatment effect across the two outcomes. Standard errors will be estimated using robust "sandwich-type" estimates to account for correlations in (possibly) multiple events within the same patient. Follow-up time will be censored at death for the non-access hospitalization outcome and at time of transplantation, transfer to a nonparticipating dialysis facility, or the end of the 12-month follow-up period for both the non-access hospitalization and death outcomes. Censoring at transplant and transfer to nonparticipating dialysis units is necessary because hospitalizations will not be recorded or classified following these events. The incorporation of death as a separate event in addition to nonaccess hospitalizations is intended, in part, to reduce the risk of bias due to informative censoring.

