The minimum detectable treatment effects under the above assumptions were estimated by statistical simulation, and are presented in Table 15a. Note that under Hochberg's procedure the threshold used to test the significance of each of the two co-primary endpoints depends on the other; hence, as indicated in the table, the minimum detectable effect size for the PHC/Mortality composite depends in part on the magnitude of the treatment effect on LV mass, and the minimum detectable effect size for the LV mass/Mortality composite depends on the size of the treatment effect on the PHC. Under a hypothesized treatment effect leading to a 20% reduction in the mortality rate, the target sample size of 250 patients has 90% power to detect treatment effects ranging from 4.59 to 4.96 points for the change in SF-36 PHC score, depending on the size of the treatment effect on LV mass. Similarly, the study has 90% power to detect treatment effects ranging from 12.1 to 13.3g for the change in LV mass, depending on the size of the treatment effect.

Table 15b provides the estimated minimum detectable effect sizes for each of the quantitative main secondary outcomes under the following assumptions: a) measurements obtained at 12 months in 80% of patients for each outcome, b) the standard deviations of the changes in each outcome (with covariate adjustment) are as indicated in the table, c) two-sided significance levels of 0.05 are applied to each outcome, without adjustment for multiple tests, d) utilization of the parametric analysis of changes with covariate adjustment as outlined in Section 9.5. The power calculations do not take into

Outcome	Treatment Effect on Other Primary Outcome 	80% power	90% power	
	0	11.3 g	13.0 g	
LVmass - Mortality	2.28 g	10.9 g	12.6 g	
	4.56 g	10.3 g	12.1 g	
	0 units	4.28 units	4.96 units	
PHC - Mortality	6 units	4.12 units	4.80 units	
	12 units	3.91 units	4.59 units	

Table 15a

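### Archive notes say prognostic covariates were dropped, but Sections 9.5 to 9.7 and 9.11 still rely on age and diabetes; the secondary analysis model is left unclear

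*Protocol*

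**What the plan says.** - **Protocol 9.5** gives the basic model for quantitative outcomes. Besides treatment, baseline value and Clinical Center, it contains the "two pre-specified baseline covariates age, and diabetic status". On purpose, it says that "the remaining terms are included to reduce residual variability and reduce bias from missing data".
- **Protocol 9.6** models non-access hospitalization or death "with treatment group and the pre-specified covariates included as independent variables", stratified by Clinical Center. Section 9.7 does the same for access patency.
- **Protocol 9.11** assumes for Table 15b that "the standard deviations of the changes in each outcome (with covariate adjustment) are as indicated in the table". It explains that the PHC, albumin and phosphorus standard deviations came from HEMO Study data after control for the baseline value and the pre-specified covariates.
- **Protocol 2.8**: "Randomization will be stratified by Clinical Center and by diabetes status".
- **Protocol 2.7** carries a bracketed note: "2014 FHN Archive Note: FHN Executive Committee dropped prognostic covariates from the analyses". **Protocol 9.9** repeats it: "FHN Executive Committee dropped prognostic covariates from the analyses". In 9.9 it directly follows the sentence that counts on prognostic baseline covariates to limit bias from missing data.

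Neither note names a covariate or an analysis. Sections 9.5, 9.6, 9.7 and 9.11 carry no such note.

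**The concern.** A reader cannot tell which model applies to the seven main secondary outcomes. Six are governed by the basic model of 9.5 and the seventh by the event model of 9.6. Age and diabetic status are the only pre-specified model covariates the protocol names, so they are the natural candidates for what was dropped.

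If they were dropped, three things follow:

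- Diabetes was used to stratify randomization but would no longer appear in the secondary models. Clinical Center stays in as an indicator or stratum; diabetes enters only through the covariate list.
- The detectable effects in 9.11 that rest on adjusted standard deviations would describe an analysis other than the one run.
- The part of the 9.9 argument that leans on baseline covariates would lose some support. This matters most for LV mass, which has a single follow-up measurement and so no 4-month value to help account for missing 12-month data.

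**Working it through.** **Inputs.** 250 patients, 1:1 (2.4, 2.8); 80% measured at 12 months (9.11), so 0.80 × 250 / 2 = 100 per arm; two-sided alpha 0.05 (Table 15b footnote); standard deviations 8.310 (PHC), 24.00 g (LV mass), 0.296 g/dL (albumin) and 1.636 mg/dL (phosphorus) from Table 15b. The protocol gives no share of variance (R²) for age and diabetes. I assume 2%, 5% and 10%.

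**Step 1: reproduce Table 15b.** Detectable effect = (z for 0.975 + z for power) × SD × √(2/n). For PHC at 80% power this is (1.960 + 0.842) × 8.310 × √(2/100) = 3.29, or 3.31 with the noncentral t distribution. At 90% power the two figures are 3.81 and 3.83. The protocol states 3.31 and 3.83. With the noncentral t, the other rows at 80%/90% power are 9.56/11.06 g for LV mass (stated 9.6/11.1), 0.118/0.136 for albumin (stated 0.12/0.14) and 0.651/0.754 for phosphorus (stated 0.66/0.77). The table is reproduced closely.

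**Step 2: remove age and diabetes.** The residual SD becomes SD / √(1 − R²), and the detectable effect rises by the same factor.

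| Assumed R² | Factor | PHC SD | PHC detectable effect, 80% power | Power at 3.31 |
|---|---|---|---|---|
| 0 (as planned) | 1.000 | 8.31 | 3.31 | 80.4% |
| 2% | 1.010 | 8.39 | 3.31 × 1.010 = 3.34 | 79.6% |
| 5% | 1.026 | 8.53 | 3.31 × 1.026 = 3.40 | 78.4% |
| 10% | 1.054 | 8.76 | 3.31 × 1.054 = 3.49 | 76.2% |

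The power column uses the normal approximation. On that same basis, at R² of 10% albumin goes from 0.117 to 0.124 g/dL and phosphorus from 0.648 to 0.683 mg/dL at 80% power.

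**Step 3: the omitted stratum.** Stratified randomization largely balances diabetes between arms. If the model then ignores diabetes, its reported variance is too large by about 1 / (1 − R²_D), where R²_D is the share explained by diabetes alone. The true two-sided error rate is about 2 × [1 − Φ(1.96 / √(1 − R²_D))]. If diabetes carries half of the assumed share (1%, 2.5%, 5%), the critical value is effectively 1.970, 1.985 or 2.011, and the error rate is 4.9%, 4.7% or 4.4% instead of 5%. Age is not a stratum and does not enter this calculation.

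**Step 4: what does not move.** Section 9.3 describes the co-primary log-rank tests with no covariates, and 9.11 powers them without adjustment, so they and Table 15a are unaffected. In Table 15b, the 24 g for LV mass is taken from a published trial, with no control for these covariates described. The Beck and Trail Making rows are expressed per 1 SD, so their entries stay the same.

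**The case against.** The strongest reply is that this is not a contradiction within the plan. The protocol is Version 2.3.1 of July 2, 2008, and without the bracketed text, 9.5, 9.6, 9.7, 9.9 and 9.11 agree with one another. The note is dated 2014 and reports a committee decision in the past tense, much as a record of changes would. It does not say that diabetes was dropped: the sentence before it in 2.7 mentions stratification separately from prognostic variables, and the final covariate list may be in a statistical analysis plan that is not at hand. Deleting the note would erase the only trace of the decision.

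Much of this stands. The loss of diabetes is an inference and has to be stated conditionally, and the note should be completed, not removed. What does not stand is that nothing needs reconciling. The notes sit inside operative paragraphs, speak of the analyses without limit, and leave the sections that define the models and their power unchanged.

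A reader might also take the PHC SD of 9.12 implied by the Table 15a footnote (2.28 / 0.25) as the unadjusted value and conclude that the detectable effect rises to 3.6 points, with power at 3.31 falling to 73%. The documents do not support that use. The footnote itself labels that SD as covariate-adjusted, and baseline value and Clinical Center would remain in the model in any case. Why 9.12 and 8.310 differ is a separate question.

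**Conclusion.** The point holds conditionally and for the secondary analyses only. The protocol leaves unclear whether age and diabetes are in the main secondary models. If the note covers them, those models omit a randomization stratum. The result is conservative standard errors, to the extent that diabetes alone is prognostic. For assumed R² of 2% to 10%, the PHC, albumin and phosphorus detectable effects rise by about 1% to 5%, with PHC at most about 3.5 points at 80% power. The R² values are assumptions; the protocol offers none.

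Two stronger readings go too far. One is that the primary analysis or its power is compromised; it never used these covariates. The other is that the missing-data argument collapses. Baseline value, Clinical Center, the 4-month responses where collected and the pattern-mixture sensitivity analysis all remain, so the argument is weakened but not removed.

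**What to change.** - Keep diabetes, as a stratification factor, and age in the secondary models of 9.5 to 9.7 as written.
- Keep the archive note, but have it state which covariates were dropped and from which analyses.
- If either covariate is dropped, restate the PHC, albumin and phosphorus rows of Table 15b. Restate the detectable reduction in non-access hospitalization or death (39% and 45%) too if it relied on adjustment. Amend the covariate sentence in 9.9 to name what remains.

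The cost is wording and, if a covariate is dropped, a short recalculation. Diabetes status is already needed for randomization and age is a baseline variable, so no new data collection is needed.

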# 9.10 Analyses of Compliance

Rates of action items, stop points, dropouts, individual missed dialysis treatments and other aspects of compliance to the treatment regimens will be summarized by treatment group and related to baseline characteristics to ascertain what factors are associated with successful implementation of the treatment regimens. Reasons for dropouts and for non-compliance to the treatment interventions will also be tabulated by randomized group to assist in determining aspects of the interventions that may need to be altered in the design of a future hard endpoint full-scale trial.

# 9.11 Statistical Power

Estimates of parameters for determination of study power were obtained primarily from the HEMO Study database. During the first year of follow-up in the HEMO Study, the mortality rate was 12%/year, the transplant rate was 4%/year, the rate of all non-access hospitalizations was 1.19 per year, and approximately 80% of patients remained in active follow-up at the 1 year assessment. Data from the HEMO Study was also used to estimate the standard deviation of the change in the PHC, average serum albumin, and average serum phosphorus after controlling for the baseline value of outcome and pre-specified covariates. The standard deviation estimate of 24 g for the change in LV mass was estimated from the standard deviation of the change in LV mass by MRI obtained in 153 patients over 9 months by Pitt et al [Pitt, 2003].

The minimum detectable effect sizes for the co-primary PHC/Mortality and LV mass/Mortality composite endpoints were estimated under the following assumptions: a) the target sample size of 250 randomized patients is achieved, b) exponentially distributed survival, with a 12%/yr mortality rate in the control group, c) exponentially distributed transplantation, with a 4%/yr transplantation rate in both treatment groups, d) measurements at 12 months of the PHC and LV mass outcomes will be obtained in 80% of randomized patients, e) normally distributed changes in the PHC and LV mass

in those patients with 12-month measurements, with standard deviations (without covariate adjustment) indicated in Table 15a, f) utilization of the log rank test as described in Section 9.3, without covariate adjustment, and g) use of Hochberg's procedure to maintain an overall Type I error rate of  $\leq 5\%$ .

The minimum detectable treatment effects under the above assumptions were estimated by statistical simulation, and are presented in Table 15a. Note that under Hochberg's procedure the threshold used to test the significance of each of the two co-primary endpoints depends on the other; hence, as indicated in the table, the minimum detectable effect size for the PHC/Mortality composite depends in part on the magnitude of the treatment effect on LV mass, and the minimum detectable effect size for the LV mass/Mortality composite depends on the size of the treatment effect on the PHC. Under a hypothesized treatment effect leading to a 20% reduction in the mortality rate, the target sample size of 250 patients has 90% power to detect treatment effects ranging from 4.59 to 4.96 points for the change in SF-36 PHC score, depending on the size of the treatment effect on LV mass. Similarly, the study has 90% power to detect treatment effects ranging from 12.1 to 13.3g for the change in LV mass, depending on the size of the treatment effect.

Table 15b provides the estimated minimum detectable effect sizes for each of the quantitative main secondary outcomes under the following assumptions: a) measurements obtained at 12 months in 80% of patients for each outcome, b) the standard deviations of the changes in each outcome (with covariate adjustment) are as indicated in the table, c) two-sided significance levels of 0.05 are applied to each outcome, without adjustment for multiple tests, d) utilization of the parametric analysis of changes with covariate adjustment as outlined in Section 9.5. The power calculations do not take into

Outcome	Treatment Effect on Other Primary Outcome 	80% power	90% power	
	0	11.3 g	13.0 g	
LVmass - Mortality	2.28 g	10.9 g	12.6 g	
	4.56 g	10.3 g	12.1 g	
	0 units	4.28 units	4.96 units	
PHC - Mortality	6 units	4.12 units	4.80 units	
	12 units	3.91 units	4.59 units	

Table 15a

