#### 9.3 Primary Outcomes

The primary analysis will evaluate the effects of the treatment interventions on two co-primary endpoints: 1) a PHC/Mortality composite endpoint based on mortality during the 1-year follow-up period and the change from baseline to 12 months in the SF-36 Rand Physical Health Composite (PHC) among those who survive to 12 months, and 2) a LV mass/Mortality composite based on mortality during the 1-year follow-up period and the change from baseline to 12 months in the Left Ventricular Mass (LV mass) as estimated by cardiac MRI among those who survive to 12 months.

The analysis of the PHC/Mortality composite will be conducted using a rank-based nonparametric procedure as follows. Patients who die prior to 12 months are ranked from lowest (indicating the poorest outcome) to highest based on their survival time prior to death. Those who survive to 12 months are ranked based on the change in the PHC score from baseline to 12 months. The patient with the largest decline in the PHC is given the next lowest rank above the patient with the latest death prior to 12 months. The patient with the largest increase in the PHC is given the highest rank, with the others falling in between. Follow-up is censored prior to 12 months if the patient is transplanted or lost to follow-up for mortality prior to the 12 assessment, and at 12 months if the patient survives to 12 months, but does not provide a 12-month PHC measurement. In this way, if a patient survives to 12 months. The ranks will be compared between treatment groups using the log-rank test which allows the integration of both survival time and a quantitative measure (e.g., the change in PHC score) in the same outcome.

The LV mass/Mortality composite will be analyzed in an analogous fashion, except that increases in LV mass will be given lower ranks (indicating a less favorable outcome) than decreases.

A variation of the Bonferroni correction due to Hochberg [Hochberg, 1988] will be used to assure that the upper limit of the studywise Type I error is approximately 0.05 for the co-primary outcomes. In this procedure both of the co-primary endpoints are regarded as statistically significant if the p-values for both outcomes are not greater than 0.05. If the larger of the two p-values is greater than 0.05, then the outcome with the smaller p-value is regarded as statistically significant if its p-value is not greater than 0.025.

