#### 9.4 Main Secondary Outcomes

As described in Section 9.3, the PHC/Mortality and LV mass/Mortality composites are the coprimary endpoints for evaluation of patient benefit in the trial. In addition, as described in Section 5.1.2, main secondary outcomes have also been designated for each of seven specific and conceptually distinct physiological or quality of life-related outcome domains. These include: i) change over 12 months in the PHC; and, ii) change over 12 months in LV mass (without the mortality components), which represent the main secondary outcomes for evaluation of the physical function and cardiac structure and function domains, respectively. The remaining outcome domains and associated main secondary outcomes are iii) depression/disease burden (change over 12 months in Beck Depression Inventory), iv) nutrition (change over 12 months in serum albumin), v) cognitive function (change over 12 months in the Trail Making Test B), vi) mineral metabolism (change over 12 months in average pre-dialysis phosphorus), and vii) clinical events (rate of nonaccess hospitalizations or death). The primary evaluation of the effects of the treatment interventions on each of these seven outcome domains will be based on the designated main secondary endpoints. Analyses of other outcomes within each domain will be regarded as exploratory. Hypertension and anemia are also stipulated as main outcome domains, but are not conducive to the designation of a single main endpoint.

Two-sided tests will be used when testing the effects of the interventions on both the primary and secondary endpoints. The primary and main secondary analyses will be conducted by intention-to-treat in the sense that all patients analyzed according to their randomized assignment, irrespective of whether they adhered to the interventions. As noted above, however, follow-up will be censored at the time of renal transplantation. The analyses of the main secondary endpoints will be tested at the 0.05 level, without formal adjustment for multiple comparisons. However, nominally significant

effects on individual secondary outcomes will be interpreted as consistent with Type I errors unless accompanied by significant effects of the interventions on the primary outcomes and a consistent pattern of treatment effects across multiple secondary outcomes.

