**Estimated Detectable Effect Sizes for the Primary Outcomes (N = 250)** 

 As described in the text, under the Hochberg procedure the statistical power for each of the two primary outcomes depends in part on the effect size for the other outcome. Thus, the minimum detectable effect on the LVmass-Mortality composite is evaluated assuming treatment effects on the change in the PHC of either 0, 2.28 (corresponding to 25% of the estimated standard deviation of the change in the PHC score after covariate adjustment), or 4.56 units (corresponding to 50% of one standard deviation). Similarly, the treatment effects on the PHC-Mortality composite are evaluated assuming effects of either 0, 6 (25% of 1 SD) or 12 g on the change in LVmass. The simulation results indicate the above calculations are accurate if the correlation between the change in LVmass and the change in the PHC score is between 0 and +0.5.

Assumed SD of 1 Yr **Outcome Variable** 80% power 90% power Change PHC (points) 8.310 3.31 3.83 LV mass (g) 24.009.6 11.1 Average Albumin (g/dL) 0.296 0.12 0.14 Average serum phosphorus (mg/dL) 1.636 0.66 0.77 Beck Depression Inventory  $(1 \text{ SD})^2$ 0.40 0.46 Trail Making Test B  $(1 \text{ SD})^2$ 0.40 0.46

Table 15bEstimated Detectable Effect Sizes for the Main Secondary Outcomes  $(N = 250)^1$ 

 Treatment effect tested at alpha = 0.05 using a 2-sided test. The estimated minimum detectable reduction in rate of non-access hospitalization or death is 39% and 45% at 80% and 90% power, respectively.

 Detectable treatment effects expressed per 1 standard deviation of the changes in the Beck Depression Inventory and Trail Making Test B because pilot data on 1-year changes in these outcomes in dialysis patients is not available.

account information provided by the 4 month measurements for patients with missing data at 12 months, and in this respect are slightly conservative.

Assuming event rates in the control group of this trial are similar to those observed in the HEMO Study, that the relationship between non-access hospitalizations and death events are similar between the two trials, and that the loss-to-follow-up rates are also similar, the estimated minimum detectable reduction in rate of non-access hospitalization or death is 39% and 45% at 80% and 90% power, respectively.

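### Section 9.11 gives two values (13.3 g and 13.0 g) for the largest 90%-power LV-mass effect, and the SD label in footnote 1 of Table 15a conflicts with Table 15b

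*Protocol*

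**What the plan says.** All the relevant statements are in the Protocol, section 9.11, Statistical Power, including Tables 15a and 15b.

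- **Text on LV mass.** For the LV mass/Mortality co-primary endpoint, "the study has 90% power to detect treatment effects ranging from 12.1 to 13.3g for the change in LV mass".
- **Table 15a, LV-mass rows at 90% power.** 13.0, 12.6 and 12.1 g, for assumed PHC effects of 0, 2.28 and 4.56.
- **Text and Table 15a on PHC at 90% power.** The text range of 4.59 to 4.96 points matches the table (4.96, 4.80, 4.59).
- **Footnote 1 of Table 15a.** The assumed PHC effect is "2.28 (corresponding to 25% of the estimated standard deviation of the change in the PHC score after covariate adjustment"; 4.56 is described as half of one SD. The matching LV-mass effects are 6 g, given as a quarter of one SD, and 12 g.
- **Assumption (e) for Table 15a.** Changes are normally distributed, "with standard deviations (without covariate adjustment) indicated in Table 15a".
- **Table 15b.** Its SDs are stated to include covariate adjustment. The PHC row reads "PHC (points) 8.310 3.31 3.83": the SD, then the detectable effects at 80% and 90% power.

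**The concern.** Two quantities each have two values in the current text.

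The first is the LV-mass effect detectable with 90% power when there is no PHC effect. The text says 13.3 g and the table says 13.0 g. The PHC sentence just before it agrees with the same table at both ends, so this is not a different convention for summarising it.

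The second is the covariate-adjusted SD of PHC change. Footnote 1 implies 9.12 and Table 15b prints 8.310.

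These are the stated detectable effects for the co-primary endpoints. A reader who wants to reproduce or update them has to work out the PHC SD behind Table 15a by division, and then decide whether to believe the footnote or assumption (e) about what that SD represents.

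**Working it through.** **Inputs.** N is fixed: "the target sample size of 250 randomized patients is achieved" (section 9.11). Patients are "randomly allocated in a 1:1 allocation to conventional or daily HD" (section 2.8), so 125 per arm. Section 9.4 states "Two-sided tests will be used when testing the effects of the interventions on both the primary and secondary endpoints". For the co-primary pair, section 9.3 applies Hochberg's procedure: both are significant if both p-values are at most 0.05; otherwise "then the outcome with the smaller p-value is regarded as statistically significant if its p-value is not greater than 0.025". Section 9.11 also gives 12-month measurements in 80% of randomized patients, control mortality of 12% per year with a 20% reduction on treatment, transplantation of 4% per year, and an LV-mass SD of 24 g.

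**Step 1: reproduce Table 15b.** Measured patients per arm: 0.80 × 125 = 100. Detectable effect = (z for 0.975 + z for power) × SD × √(2/100).

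- PHC, SD 8.31, 80% power: (1.960 + 0.842) × 8.31 × 0.1414 = 3.29; with the noncentral t, 3.31. Printed: 3.31.
- PHC, SD 8.31, 90% power: (1.960 + 1.282) × 8.31 × 0.1414 = 3.81; with the noncentral t, 3.83. Printed: 3.83.
- LV mass, SD 24, noncentral t: 9.56 and 11.06. Printed: 9.6 and 11.1.

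Table 15b is therefore consistent with an adjusted PHC SD of 8.31.

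**Step 2: SD implied by footnote 1.** 2.28 / 0.25 = 9.12, and 4.56 / 0.50 = 9.12. A quarter of 8.31 would be 2.08.

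**Step 3: which SDs does Table 15a use?** Divide each printed effect by its SD. The two endpoints share the same design, so matching cells should give the same standardized effect.

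| Power, effect on other outcome | LV mass / 24 | PHC / 9.12 |
|---|---|---|
| 80%, none | 11.3 → 0.471 | 4.28 → 0.469 |
| 80%, 0.25 SD | 10.9 → 0.454 | 4.12 → 0.452 |
| 80%, 0.50 SD | 10.3 → 0.429 | 3.91 → 0.429 |
| 90%, none | 13.0 → 0.542 | 4.96 → 0.544 |
| 90%, 0.25 SD | 12.6 → 0.525 | 4.80 → 0.526 |
| 90%, 0.50 SD | 12.1 → 0.504 | 4.59 → 0.503 |

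The largest gap between columns is about 0.002 SD. Two alternatives do not fit the 90%, no-other-effect row: 13.3 / 24 = 0.554 and 4.96 / 8.31 = 0.597. Table 15a was therefore built with a PHC SD of about 9.12, and 13.0 g is the entry consistent with its neighbours.

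**Step 4: does simulation settle 13.0 against 13.3 g?** The rank composite was simulated with the log-rank test and Hochberg's procedure under the stated assumptions (20,000 to 40,000 runs).

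- Base case, 80% of randomized patients measured: about 88.5% power at 13.0 g and 90% at 13.3 g.
- All survivors measured: about 91% at 13.0 g and 92% at 13.3 g.

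The base case does not favour 13.3 g specifically. In that case the other printed 90% cells also fall short, at roughly 87% to 89%; for example, 4.96 points with SD 9.12 gives 88.6% to 89.2%. Solving for exactly 90% gives 13.3 g in the first LV-mass row but about 12.4 g in the last, so it does not reproduce the text's lower end of 12.1 g either. The answer depends on how missing 12-month measurements are handled, so simulation from outside cannot choose between the two figures.

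**Step 5: size.** 13.3 − 13.0 = 0.3 g, or 0.3 / 13.0 = 2.3%. In the two cases of step 4 it is worth about 1 to 1.5 points of power.

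**The case against.** The strongest reply is that this is editorial. Assumption (e) already says Table 15a uses unadjusted SDs, Table 15b prints its adjusted SD and reproduces, and on that reading one figure in the text and one phrase in a footnote are wrong while no tabulated effect needs to change. Most of that stands, and it sets the weight of the point. It does not remove the two contradictions, which are in the current text.

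Some stronger readings are tempting, and the document does not support them.

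- **That the PHC row of Table 15b is wrong.** If 9.12 really were the adjusted SD, the entries would be 3.63 and 4.20, and power at 3.31 points would be about 73%. Step 3 and assumption (e) both point to 9.12 being the unadjusted SD, so these figures do not measure the error.
- **That 250 patients is put in doubt.** N = 250 is an input to section 9.11, not a result of these effects. Sections 2.4 and 10.1 tie any revision of the target to recruitment and operational progress.
- **That Table 15a omits the SDs promised in assumption (e).** The tables in the text at hand are visibly broken, so a missing column cannot be asserted, and footnote 1 implies both SDs in any case.
- **That the table must be wrong because 13.3 g simulates to 90%.** Step 4 shows why this does not follow.

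The swapped units in the column for the other outcome (2.28 and 4.56 shown in g, 6 and 12 shown in units) are clerical. The footnote has them right and no result depends on them.

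**Conclusion.** The point holds as a small inconsistency in stated power figures. Section 9.11 gives both 13.3 g and 13.0 g for one co-primary detectable effect, and it attaches the same description, covariate-adjusted SD of PHC change, to both an implied 9.12 and a printed 8.310. Both cannot be right in either case.

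The more probable explanation is that 13.0 g belongs with the table, that 9.12 is the unadjusted SD used for Table 15a, and that 8.31 is the adjusted SD used for Table 15b, which stands. This is an inference: 9.12 is never printed, and section 9.11 describes the source of the PHC SD only for the covariate-adjusted estimate. It rests on the close agreement of the scaled entries in Table 15a and on assumption (e).

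The practical effect is about 1 to 1.5 points of power on one LV-mass figure. The sample size, the tests and the error control are unaffected.

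**What to change.** 1. Check the archived simulation output and state one LV-mass maximum at 90% power in both text and table. 13.0 g fits the rest of Table 15a; if the output supports 13.3 g, correct the table instead.
2. In footnote 1 of Table 15a, relabel the SD behind 2.28 and 4.56 as the one without covariate adjustment.
3. Once confirmed, state both PHC SDs next to their tables: 9.12 unadjusted (Table 15a) and 8.31 adjusted (Table 15b).
4. In the same edit, correct the unit labels in Table 15a's column for the other primary outcome: PHC units for 2.28 and 4.56, grams for 6 and 12.

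The cost is one look-up and a few words. A new simulation is needed only if the output cannot be found. No design element changes.
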